Experimental Procedure (Aim 1 and 2): Screening Visit – Consent. Participants will receive a series of assessments designed to evaluate nicotine dependence and use, psychiatric conditions, and mood. These include a standard MUSC clinical intake evaluation screen for research (used in other studies by the PI and Co-I), MINI International Neuropsychiatric Interview (88), TLFB (89), Beck Depression Inventory II (90), State-Trait Anxiety Inventory (91) and Profile of Mood States (92). Data will be collected using REDCap™, and entered directly into the online portal to ensure security and prevent data loss. Study Visit Procedures: At all visits, individuals will provide a urine screen to detect recent use of drugs of abuse and pregnancy, a breath carbon monoxide (CO) sample to detect recent cigarette smoking, and a breath sample to test for recent alcohol use. At visits 1, 6, 10 and follow up visits (Assessment visits), participants will complete a battery of behavioral assessments following active TMS or sham (see Table 2). MRI scanning (at visits 1 and 10) will occur prior to TMS in order to isolate cumulative, rather than acute, effects of TMS. At all visits participants will be required to provide a CO reading at least 50% of their baseline CO measure to ensure they are at least 6 hours deprived from cigarettes. Cigarette deprivation will be used to increase craving and responding for cigarettes. Short term cigarette deprivation has known amplification effects on the brain response to smoking cues (93, 94). Moreover, we have extensive experience with successfully using this deprivation procedure (33, 41).

TMS Procedures. After the MRI scans participants will be escorted into the Brain Stimulation room (30 feet away) where scalp localization will be performed for the TMS procedure. The Cartesian position of the coil (X,Y,Z) will be determined by standardized positions from the EEG 10-20 system: 1) FP1 will be

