Statistical Analysis Plan.

Data analysis plan: Data for this study will be acquired by the members of the [name] lab including graduate students and research specialists. These individuals will also perform data under the guidance of the PI. Manuscript composition will be led by the PI, with the assistance of the research team.

Prior to formal statistical analysis, summary statistics for all variables will be obtained and spaghetti plots will be generated. All behavioral outcome measures will be based on standardized composite scores from the literature. We will also use data reduction techniques (such as factor analysis or principle component analysis) to confirm the applicability of the composite scores in our population. Analyses will be performed for each phase separately.

Behavioral Outcomes: For the treatment phase (10 days of real/sham TBS), the behavioral outcomes include Cigarette demand (Q0 and alpha), Craving (QSU Intention, QSU Relief), and Delay Discounting (\$100 and \$1000). For the treatment phase the analysis will be performed using repeated measures ANOVA on change scores from baseline for each visit. The main independent variable in the ANOVA will be time (visits on day 1, 6, 10), group (real or sham) and their interaction. For correlations of observations across visits an AR(1) structure will be considered and compared with other structures such as compound symmetry and a general structure. The primary hypothesis is the interaction. If the interaction effect for an outcome is significant, we will conclude there is statistical evidence of overall treatment effect. If the spaghetti plots suggest trends (e.g., linear, quadratic, or piecewise changes) we will treat time as a continuous variable and fit repeated measures regression models along with group and its interaction with continuous time as independent variables.

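### Baseline is neither defined nor used as a covariate in the change-score model; if it is day 1, the listed general covariance cannot be fitted and standard errors for the day-10 group difference are too small

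*Combined protocol and SAP*

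**What the plan says.** The SAP (Behavioral Outcomes) analyses cigarette demand, craving and delay discounting in the treatment phase by "repeated measures ANOVA on change scores from baseline for each visit". It then states: "The main independent variable in the ANOVA will be time (visits on day 1, 6, 10), group (real or sham) and their interaction". For the within-person correlation, "an AR(1) structure will be considered and compared with other structures such as compound symmetry and a general structure". The test that decides the matter is named plainly: "The primary hypothesis is the interaction". Baseline is not defined for these outcomes, and the baseline score does not appear among the model terms.

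The protocol (Experimental Procedure, Study Visit Procedures) schedules the measurements: "At visits 1, 6, 10 and follow up visits (Assessment visits), participants will complete a battery of behavioral assessments following active TMS or sham". The screening tools it names are a standard clinical intake evaluation, a psychiatric interview, a smoking timeline, and depression, anxiety and mood scales. None of the analysed outcomes is among them. MRI at visits 1 and 10 is placed before stimulation, so that cumulative and not acute effects are measured.

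**The concern.** On the visible text, day 1 is the only candidate for baseline. If so, the day-1 change is zero for every participant, yet day 1 remains a response level. Two things follow. The general covariance structure has a row and column of zeros and cannot be estimated, so the promised comparison of structures cannot be completed. Structures with one common variance average a zero with two real variances, so the model takes the day-6 and day-10 changes to be less variable than they are.

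The interaction alone tells a reader neither the direction of a difference nor the visit at which it occurs. A real-sham difference at day 10 is the natural follow-up, and its interval would be too narrow.

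Separately, whichever measurement is baseline, subtracting it without adjusting for it discards precision that the trial has already paid for.

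**Working it through.** **Inputs.** From the documents: 138 participants over two aims; time levels 1, 6 and 10; candidate structures AR(1), compound symmetry (CS) and general; primary test group-by-time, 2 df. The documents give no per-arm size, alpha, SD, correlation, effect or power, so there is no figure of the plan's own to reproduce. Assumed: 138/2 = 69 per aim, split 35 and 34; alpha 0.05 two-sided; raw SD 1; raw correlation ρ between visits, CS or AR(1); no dropout. Steps 1 to 3 assume that day 1 is the baseline.

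**1. General structure.** The responses are (0, y6 − y1, y10 − y1). Their covariance has a zero row, so its determinant is 0 and the likelihood has no maximum. With the day-1 variance set to 1e-2, 1e-4 and 1e-8, −2 log L per df is −2.9, −7.5 and −16.7, and it keeps falling.

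**2. Marginal real-sham difference at a visit.** With balanced data and a free mean for each group and visit, the CS fit estimates one variance, the average of the three.

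- Raw CS: true variances 0, v, v with v = 2(1 − ρ). Pooled value 2v/3. SE ratio √(2/3) = 0.816 at both visits for any ρ, 18% too small. An AR(1) fit, solved numerically, gives 0.810, 19% too small.
- Raw AR(1): true variances 0, 2(1 − ρ), 2(1 − ρ²). The SE ratio under a CS fit is √[(2 + ρ)/(3(1 + ρ))] at day 10 and √[(2 + ρ)/3] at day 6.

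| Raw AR(1) ρ | Day 10, CS fit | Day 10, AR(1) fit | Day 6, CS fit | Day 6, AR(1) fit |
|---|---|---|---|---|
| 0.3 | 0.768 | 0.762 | 0.876 | 0.869 |
| 0.5 | 0.745 | 0.741 | 0.913 | 0.907 |
| 0.7 | 0.728 | 0.725 | 0.949 | 0.945 |
| 0.9 | 0.713 | 0.712 | 0.983 | 0.982 |

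For ρ of 0.5 to 0.7 the day-10 SE is therefore about 25-27% too small. Day 6 is 2-13% too small over the whole range.

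Type I error of the day-10 difference is about 2Φ(−1.96 × ratio): 11.0% at 0.816, 14.4% at 0.745, 15.6% at 0.725. Simulation with raw CS and 34 per arm gave 10.7-10.8%.

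**3. Primary interaction.** Under CS the interaction F is identical for raw and change scores (checked on two data sets: 0.0800 both ways, 0.4211 both ways). Simulated type I error was 5.1-5.3%, and with a misspecified structure about 5-5.5%. Under CS the zero row costs the interaction no power. An AR(1) fit to raw-CS data costs about 2-6 points.

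**4. Efficiency.** Raw CS, effect growing linearly to 0.5 SD at day 10 (0, 0.25, 0.5), w = 1/35 + 1/34 = 0.0580.

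- Interaction, 2 and 134 df: noncentrality 0.125/[(1 − ρ)w] = 4.31 (ρ = 0.5) or 7.19 (ρ = 0.7).
- Day-10 change, t on 67 df: 0.5/√[2(1 − ρ)w] = 2.08 or 2.68.
- Day-10 ANCOVA, t on 66 df: 0.5/√[(1 − ρ²)w] = 2.40 or 2.91.

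| Test | ρ = 0.5 | ρ = 0.7 |
|---|---|---|
| Planned 2-df interaction | 44% | 66% |
| Day-10 change, unadjusted | 53% | 75% |
| Day-10 ANCOVA | 66% | 82% |

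The step from the first row to the second comes from testing 1 df instead of 2. The step from the second to the third is the gain from adjustment: the SE shrinks by the factor √[(1 + ρ)/2], which is 0.87 or 0.92.

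**5. Dropping day 1 alone.** The remaining interaction is the day-10 minus day-6 contrast. If the effect is the same at both days, that contrast is 0 and power equals alpha, 5%. With 34 per arm, ρ = 0.5 and a constant 0.5 SD effect, the other tests have: planned interaction 55%, baseline-adjusted joint 2-df test 72%, baseline-adjusted mean of days 6 and 10 82%.

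**The case against.** The strongest reply is that the premise is inferred. The SAP never says that day 1 is the baseline, and change from baseline at day 1 makes sense if an earlier score exists. The list of screening tools is worded as inclusive, not exhaustive. Tables 1 and 2, which hold the schedule and the battery, are not in the available text. The CO rule applied at every visit refers to a baseline CO measure, which hints at pre-visit-1 data of some kind, though not for these outcomes. All of this stands: steps 1 to 3 are conditional, and with a separate baseline they do not arise.

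A reader might infer that the primary test is invalid. It is not: the interaction keeps its size, and the inflated error belongs to a marginal day-10 difference that the SAP does not name as a planned contrast. A reader might also take the 18-27% shortfall to apply at every visit. It does not: under raw AR(1), day 6 is affected far less. Nor does the zero row explain the power gap, since under CS it costs the interaction nothing.

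The SAP also allows continuous time if plots suggest a trend. Under the linear effect assumed here, a 1-df slope test has about 54% power (ρ = 0.5) or 76% (ρ = 0.7), which closes roughly half of the gap to ANCOVA or more. That stands too, but the choice depends on inspecting the data.

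Finally, the list of structures is open ("compared with other structures such as compound symmetry and a general structure"), and a failed general fit would be noticed. A structure with a separate variance at each visit would, however, also drive the day-1 variance to zero, and the SAP offers no way round this.

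**Conclusion.** The point holds in conditional form. What is certain is that baseline is undefined, that its score is not a covariate, and that the first visible battery of these outcomes follows the first stimulation. If day 1 is the baseline, the general structure cannot be fitted, and equal-variance structures understate the day-10 SE by 18-19% (raw CS) or about 25-27% (raw AR(1), correlation 0.5-0.7), with type I error near 11% or 14-16% for that difference. The primary interaction is sound in size.

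The efficiency loss from not adjusting does not depend on which measurement is baseline. At day 10 it is about 12 points of power at correlation 0.5 and 6-7 points at 0.7. These power figures rest on assumed arm sizes, alpha, effect and compound symmetry.

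**What to change.** State in the SAP which measurement is baseline for each outcome, and whether it is taken before or after the first stimulation.

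- **If baseline is day 1:** remove day 1 from the response. Model day-6 and day-10 scores with the baseline score as covariate, group, visit and group-by-visit, and an unstructured 2×2 covariance (REML). Replace the interaction as primary with a test of the adjusted group effect: either the joint 2-df test over days 6 and 10 or one prespecified contrast. Removing day 1 while keeping the interaction primary would be worse than the present plan for a constant effect (step 5).
- **If baseline is a separate pre-treatment measure:** keep day 1 as a response and add the baseline score as covariate. With one common slope the gain falls on the group differences; the interaction among days 1, 6 and 10 is essentially unchanged.

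The cost is SAP wording and, in the first case, a changed primary contrast. One limit remains. If the day-1 score is taken after stimulation, adjusting for it can remove any acute first-session effect, as the planned subtraction also can. The SAP should say so.

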**QuitFast: Evaluating Transcranial Magnetic Stimulation as a
Tool to Reduce Smoking Directly Following a Quit Attempt**

PI: [name].

NCT: NCT03576768

Unique Protocol ID: 00074769

IRB Approval Date: 06/11/2019

Protocol & Statistical Analysis Plan

Protocol.

Overview. We will parametrically evaluate the efficacy of two promising TMS treatment strategies (LTD-like stimulation to the vmPFC (Aim 1), LTP-like stimulation to the dlPFC (Aim 2)) as tools to change smoking behavior and brain reactivity to smoking cues. These aims will be addressed in serial (Aim 1 Years 1-2, Aim 2 Years 3-4). A randomized, double-blind, sham-controlled design will be used for each aim.

In total, 138 smokers will be recruited from the tri-county area surrounding Charleston, SC. Current cigarette smokers seeking to quit smoking and willing to set a quit date will be recruited from the tri-county area (Charleston, Berkeley, Colleton County) using digital and print advertising in diverse media outlets. Following informed consent and screening, participants will be randomized to receive real or sham TMS to the vmPFC (Aim 1, Years 1-2) or the dlPFC (Aim 2, Years 3-4) via a Central Randomization Core (run by the MUSC Data Coordination Unit (see Table 1 and TMS Procedures below for more details regarding sham controls and double blinding procedure).

During the Treatment Phase, participants will receive 10 sequential days of TMS (with additional behavioral and MRI scanning (see Table 1). Participants will be allowed to miss up to 2 TMS visits in a row but all 10 visits must be completed in 14 days.

During the Follow Up Phase, behavioral assessments will be acquired weekly for the first 4 weeks (see Table 1), and daily EMA will be acquired. Additionally weekly EMA assessments will be acquired for 24 weeks (approx. 6 months from quit date).

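### Outcome plots choose the form of the primary interaction test, which can raise the per-outcome false-positive rate from 5% to about 6-7.5%, or about 10%, if the plots show group

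*Combined protocol and SAP*

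**What the plan says.** All the relevant text is in the SAP: the introductory paragraphs of the data analysis plan and the Behavioral Outcomes paragraph.

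- Looking comes first: "Prior to formal statistical analysis, summary statistics for all variables will be obtained and spaghetti plots will be generated".
- The response is a change score: "the analysis will be performed using repeated measures ANOVA on change scores from baseline for each visit".
- The default model has three visits as levels of time: "The main independent variable in the ANOVA will be time (visits on day 1, 6, 10), group (real or sham) and their interaction".
- The primary test and how it is read: "The primary hypothesis is the interaction", and "If the interaction effect for an outcome is significant, we will conclude there is statistical evidence of overall treatment effect".
- The switch: "If the spaghetti plots suggest trends (e.g., linear, quadratic, or piecewise changes) we will treat time as a continuous variable". The model then becomes a repeated measures regression with group and its interaction with continuous time.

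The SAP does not say what counts as a trend or how to choose among the three shapes. It does not say whether a joint or a single-term interaction test is primary after the switch, or whether the plots identify the arms. It states no alpha and does not define the baseline.

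**The concern.** A significance test keeps its stated error rate if its form is fixed in advance, or is chosen using information unrelated to the contrast tested. Here the contrast is the difference between real and sham in their course over time. If someone sees that difference plotted by arm and then picks the time coding that suits it, the choice favours a small p-value.

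The rule bears on the primary hypothesis. It can be applied separately to each of six treatment-phase outcomes (two demand indices, two craving scales, two discounting tasks) in each of two aims. A significant interaction on any outcome is to be read as evidence of a treatment effect, so a positive result could partly reflect the choice of coding.

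**Working it through.** **Inputs from the documents.** Three visits (days 1, 6, 10); the interaction as the primary test; 138 participants over two aims (protocol Overview).

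**Assumptions, because the documents are silent.** Two-sided alpha 0.05 per outcome; 138 / 2 = 69 per aim, split 35 v 34; within-person correlation 0.3 to 0.7 under autoregressive or compound-symmetric covariance; complete data; a baseline measured before day 1. Subtracting the same baseline from all three visits leaves within-person contrasts between visits unchanged, so the baseline's own value does not affect the interaction. The SAP states no error rate, so there is no figure of its own to reproduce.

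**Approximation by hand.** Split the group difference in time course into two orthogonal parts, linear (Z1) and curved (Z2). Treat them as independent standard normals under the null, which is exact under compound symmetry with large samples. The linear test rejects when |Z1| > 1.96. The joint 2-df test rejects when Z1² + Z2² > 5.99.

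1. *Either form fixed in advance:* 5%.
2. *Linear test if |Z1| exceeds a visual threshold c, otherwise the 2-df test.* The rate is 0.05 + P(|Z1| < c and Z1² + Z2² > 5.99). For c = 1.0 this is 6.2%; for c = 1.5 it is 6.8%.
3. *Linear test if the difference looks more linear than curved (|Z1| > |Z2|), otherwise the 2-df test.* By symmetry each branch is taken half the time. The linear branch rejects with probability ½(1 − 0.95²) = 4.875% and the 2-df branch with ½ × 5% = 2.5%. The total is 7.4%.
4. *Smaller p of the linear and 2-df tests (rule 2 with c = 1.96):* 7.5%.
5. *Single-term linear or single-term quadratic test, whichever looks larger:* 1 − 0.95² = 9.75%.

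**Null simulation** (40,000 trials per scenario, 35 v 34, days 1, 6, 10):

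| How the form is chosen | False-positive rate |
|---|---|
| Fixed 2-df test, general covariance | 4.8-5.1% |
| Fixed linear test | 4.9-5.1% |
| From the time trend pooled over group | 4.8-5.2% |
| Group-labelled: linear if the slope difference looks sizeable, otherwise 2-df | 6.0-7.0% |
| Group-labelled: linear if the difference looks more linear than curved, otherwise 2-df | 7.2-7.5% |
| Smaller p of 2-df and linear, general covariance | 7.3-7.7% |
| Group-labelled: larger-looking of single-term linear and quadratic | 9.6-10.0% |

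The simulation agrees with the hand calculation. A run with 69 v 69 gave nearly the same figures, so sample size is not what drives the result.

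**Why pooled or masked plots are harmless.** Under the null the arm labels are exchangeable. What is seen without them says nothing about the difference between arms.

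**Which forks are real.** Three visits have two degrees of freedom for shape. A full quadratic, or a piecewise line with its knot at day 6, uses both. With the same covariance structure, its joint group interaction is the same 2-df test as categorical time. If interactions are tested jointly, the only real fork is categorical versus linear (rules 2 to 4). Rule 5 needs single-term tests.

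**If day 1 is the baseline.** Its change score is zero for everyone, leaving days 6 and 10. The categorical and linear interactions are then the same 1-df test and there is nothing to choose.

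**The case against.** The strongest reply is that the SAP speaks of shapes over time, not of arms diverging. A spaghetti plot of all participants in one panel would serve its purpose, and a choice made that way leaves the error rate at about 5%. That is correct. A reader might infer that the plan necessarily inflates the error rate to 7-10%; the documents do not support that, because they never say that the plots are split by group. Equally, they never say that the plots are pooled or masked. The SAP has members of the investigator's laboratory analyse the data, and no masking at the analysis stage is described.

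Three other stronger readings also fail:

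- That the quadratic and piecewise options each add inflation. Tested jointly, the saturated versions add none. About 10% requires single-term tests, which the SAP neither specifies nor excludes.
- That the rate is 13% or more. Such figures come from trying every shape and covariance structure and keeping the smallest p. The SAP describes looking at plots, not that. It does leave the covariance open ("an AR(1) structure will be considered and compared with other structures such as compound symmetry and a general structure"), but that is a separate choice.
- That testing six outcomes makes this worse. Multiplicity is a separate issue and lends no weight here.

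The baseline objection stands in part. Listing day 1 as a level of time suggests that it is not the baseline, and the protocol's Experimental Procedure places the visit 1 battery after stimulation. But the baseline is not defined, so the possibility that the fork does not exist cannot be ruled out.

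**Conclusion.** The concern holds in conditional form. The gap in the wording is certain: the form of the primary test depends on outcome plots, with no criterion and no masking requirement. Its size depends on how the plots are used. At an assumed two-sided 0.05 with three analysed visits, the per-outcome rate is about 5% with pooled or masked plots. It is about 6-7.5% if group-labelled plots steer between the categorical and linear tests, and about 10% if single-term tests are matched to the observed difference. It is 5%, with no inflation from this source, if day 1 is the baseline. The alpha, the allocation, the size per aim and the correlation are assumptions; the results vary little over the sample sizes and correlations tried. The point should be corrected before analysis, but it does not by itself invalidate the design.

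**What to change.** Amend the Behavioral Outcomes paragraph to say three things:

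1. For every outcome, the primary test is the joint group-by-time interaction with time as a categorical factor. Alternatively, the coding is chosen by a stated objective rule applied to data masked to group.
2. Whether day 1 is the baseline and, if not, when the baseline is measured.
3. Linear, quadratic and piecewise models are sensitivity or exploratory analyses and cannot replace the primary test.

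The interaction can remain the primary hypothesis; moving to a single-visit contrast is a matter of preference that this correction does not need.

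The cost is a few sentences and a small loss of power if change is truly linear, because the joint test spends two degrees of freedom where a linear test spends one. The plots can still be made and reported.
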